4.2.2 Dose and Administration

Study treatment must not be administered as an IV push or bolus. Study treatment will be administered by outpatient IV infusion given over approximately 30 minutes on Day 1 of each 21-day cycle. In the absence of infusion toxicities, the infusion rate for all patients should be calculated in order to achieve a 30-minute infusion period. Study treatment will be administered through a dedicated IV line and cannot be mixed with other medications.

The dose of study treatment is 1.8 mg/kg. Chemical and physical stability of the reconstituted brentuximab vedotin drug product has been demonstrated for 24 hours. Opened and reconstituted vials should be used immediately. If not used immediately, the in-use storage should not be longer than 24 hours. In case infusion is interrupted, the interruption cannot be more than 24 hrs from the time of reconstitution of the drug.

Patients with treatment-associated Grade 2 peripheral neuropathy will follow dose modification as specified in **Table 1** in **Section 4.2.5**. **Dosing is based on patient weight on Cycle 1 Day 1** according to the institutional standard; however, doses will be adjusted for patients who experience a $\geq 10\%$ change in weight from baseline. Actual weight will be used except for patients weighing greater than 100 kg; dose will be calculated based on 100 kg for these individuals. The dose will be rounded to the nearest whole number of milligrams (Seattle Genetics, 2010).

Patients will be observed on day 1 for close monitoring of potential side effects of drug therapy and/or disease-related symptoms due to mast cell mediator release (eg, hypotension, anaphylactic shock) for at least 60 minutes after completion of the infusion. Intensive care equipment (eg, crash cart) and/or facilities must be readily available for these trial patients.

4.2.3 Required Pre-medication and Post-medication

Routine premedication should not be administered prior to the first dose of study treatment. However, patients who experience a Grade 1 or 2 infusion-related reaction may receive subsequent study treatment with premedication as described in **Section 4.2.4** below.

4.2.4 Management of Infusion Reactions

Infusion-related reactions may occur during the infusion of study treatment. The infusion is to be administered at a site properly equipped and staffed to manage anaphylaxis should it occur. The patient should be observed for at least 60 minutes following the first infusion of study treatment. During this observation period, the IV line should remain open for at least 1 hour to allow administration of IV drugs if necessary. All supportive measures consistent with optimal patient care will be given throughout the study according to institutional standards. This includes adjusting the infusion time if necessary. Medications for infusion-related reactions should be readily available.

Patients who experience a Grade 1 or 2 infusion-related reaction may receive premedication for the current or future potential infusion reactions consisting of acetaminophen (650 mg orally) and diphenhydramine (25 to 50 mg orally or 10 to 25 mg IV) or according to institutional standards, administered 30 to 60 minutes prior to each 30-minute infusion.

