4.2.5 Dose Modifications

Intra-patient dose reduction to 1.2 mg/kg will be allowed depending on the type and severity of toxicity. **Table 1** describes the recommended dose modifications for study treatment-associated toxicity (toxicity with suspected relationship to SGN-35).

Peripheral Neuropathy: Peripheral neuropathy should be managed using a combination of dose delay and reduction to 1.2 mg/kg. For new or worsening Grade 2 or 3 neuropathy, dosing should be held until neuropathy improves to Grade 1 or baseline and then restarted at 1.2 mg/kg. For Grade 4 peripheral neuropathy, SGN-35 should be discontinued.

A study of brentuximab vedotin (SGN-35) in CD30-positive systemic mastocytosis with or without an associated hematological clonal non-mast cell lineage disease (AHNMD)

Neutropenia: Neutropenia should be managed by dose delays and reductions. The dose of SGN-35 should be held for Grade 3 or 4 neutropenia until resolution to baseline or Grade 2 or lower. Growth factor support should be considered for subsequent cycles in patients who experience Grade 3 or 4 neutropenia. In patients with recurrent Grade 4 neutropenia despite the use of growth factors, discontinuation or dose reduction of SGN-35 to 1.2 mg/kg may be considered.

Acute Pancreatitis: Acute pancreatitis has been identified as an important potential risk associated with brentuximab vedotin dosing. Dosing should be held until a diagnosis of acute pancreatitis has been excluded if clinically suspected.

The start of the next cycle may be delayed for up to 30 days if additional time is required for the patient to recover from study treatment-associated toxicity experienced during the current cycle (**Table 1**). Delays of greater than 30 days are prohibited without approval of the Principal Investigator of the entire study, [name].

Doses reduced for treatment-related toxicity should not be re-escalated.

If 4 out of the 11 patients experience emergent drug-related Grade 3 or 4 non-hematologic toxicity, the study will be placed on hold for safety review, and if restarted upon study amendment, the starting dose of therapy for subsequent patients would be no more than 1.2 mg/kg.

Table 1. Dose Reduction Algorithms for Non-Hematologic and Hematologic Toxicity With Suspected Relationship to SGN-35

Toxicity	Grade 1	Grade 2	Grade 3	Grade 4

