Non-Hematologic	Continue at same dose level.	
Continue at same dose level, except in the event of Grade 2 neuropathy.
 
For Grade 2 neuropathy, withhold dose until toxicity is \leq Grade 1 or has returned to baseline, then reduce the dose to 1.2 mg/kg and resume treatment.
 
If Grade 2 neuropathy recurs at a dose of 1.2 mg/kg, the patient should be discontinued from study.
	
Withhold dose until toxicity is \leq Grade 1 or has returned to baseline, then resume treatment at the same dose level. ^a
 
If the toxicity has not returned to \leq Grade 1 after holding the dose for 30 days, then the patient should be discontinued from the study.
 
If the same Grade 3 toxicity recurs, withhold dose until toxicity is \leq Grade 1 or has returned to baseline, then reduce to the 1.2 mg/kg/level. ^a
 
For patients with recurrence of the same Grade 3 toxicity, the patient should be discontinued from the study.
 
For Grade 3 neuropathy, withhold dose until toxicity is \leq Grade 1 or has returned to baseline, then reduce the dose to 1.2 mg/kg and resume treatment.
 
If Grade 3 neuropathy recurs at a dose of 1.2 mg/kg, the patient should be discontinued from study.
	
Withhold dose until toxicity is \leq Grade 1 or has returned to baseline, then reduce dose to 1.2 mg/kg and resume treatment. ^a
 
If the toxicity has not returned to \leq Grade 1 after holding the dose for 30 days, then the patient should be discontinued from the study
 
For patients with recurrence of the same Grade 4 toxicity at a dose of 1.2 mg/kg, the patient should be discontinued from the study
 
For Grade 4 neuropathy, SGN-35 should be discontinued.

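### After a drug-related Grade 3–4 infusion reaction or anaphylaxis nothing requires stopping SGN-35, and Table 1's general default is to resume after recovery

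*Combined protocol and SAP*

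**What the plan says.** **Preparedness, any grade.** Section 4.2.2 requires observation on day 1 for drug side effects and for "disease-related symptoms due to mast cell mediator release (eg, hypotension, anaphylactic shock"), with intensive care equipment at hand. Section 4.2.4 adds: "The infusion is to be administered at a site properly equipped and staffed to manage anaphylaxis should it occur". It also asks for 60 minutes of observation after the first infusion, an open IV line, supportive care to institutional standards and an adjustable infusion time.

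**Later doses, Grade 1–2 only.** Under Section 4.2.3, "patients who experience a Grade 1 or 2 infusion-related reaction may receive subsequent study treatment with premedication as described in" Section 4.2.4. The matching sentence there is "Patients who experience a Grade 1 or 2 infusion-related reaction may receive premedication for the current or future potential infusion reactions". Neither section says what follows a Grade 3 or 4 reaction.

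**General dose rule.** Section 4.2.5 says that Table 1 "describes the recommended dose modifications for study treatment-associated toxicity", meaning toxicity suspected to be related to SGN-35. In the non-hematologic row, a Grade 3 event is held until it is Grade 1 or less or "has returned to baseline, then resume treatment at the same dose level". A Grade 4 event is held to the same recovery point, "then reduce dose to 1.2 mg/kg and resume treatment". Grade 4 neuropathy leads to discontinuation at the first event. Footnote a gives electrolyte abnormalities their own rule. Infusion reactions have no entry of their own.

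**The concern.** The plan prepares sites for anaphylaxis but does not say whether a patient who has had it may be dosed again. The rule that fills the gap was written for toxicities where recovery is a sensible test of fitness to continue. For an acute infusion reaction it is the wrong test: the event may settle well before the next dose, and the danger lies in the next exposure.

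A site that follows the written rules would re-expose a patient after a severe or life-threatening drug reaction. Premedication is specified only after the mild reactions. The entry criteria exclude known hypersensitivity to an excipient, but no on-treatment rule stops a patient who shows a severe reaction to the infusion.

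**Working it through.** The plan states no figure on this point, so the check is mainly a reading of every section that could govern a further dose.

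**1. Which rule applies to a drug-related Grade 3–4 infusion reaction?**

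| Source | Covers the event? | Consequence for the next dose |
|---|---|---|
| 3.3.2, excipient hypersensitivity | Entry only | None on treatment |
| 4.2.2, observation | Yes | None stated |
| 4.2.3 and 4.2.4, premedication | Grade 1–2 only | None stated for Grade 3–4 |
| 4.2.4, preparedness and supportive care | Any grade | None stated |
| 4.2.5, hold at 4 of 11 patients | Counts the event | Acts on the study, not the patient |
| Table 1, non-hematologic row | Yes, if SGN-35 is suspected | Resume after recovery |
| 4.3, discontinuation | Adverse event is a listed reason | CRF category, no trigger |

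Only Table 1 gives a patient-level dosing instruction. If the reaction is attributed to mast cell mediator release alone, Table 1 falls outside its own scope and no written re-dosing rule remains.

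**2. What does Table 1 recommend?**

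- First Grade 3 event: resume at the same dose, which is 1.8 mg/kg if there was no earlier reduction. The cell then says both that a recurrence leads to 1.2 mg/kg and that "For patients with recurrence of the same Grade 3 toxicity, the patient should be discontinued from the study". Under either reading, the first event is followed by one recommended exposure at the same dose.
- First Grade 4 event: resume at 1.2 mg/kg, which is 1.2/1.8 = 67% of the starting dose. A stop is written for recurrence at that dose, or for failure to recover after a 30-day hold.
- Cycles last 21 days. If the reaction has settled before the next infusion is due, the hold delays nothing.

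**3. How many infusions remain?** After a cycle 1 reaction that does not recur, 8 − 1 = 7. With re-treatment in cycles 9–16, 7 + 8 = 15. The larger figure needs a response still present at completion of cycle 8, followed by loss of response (Sections 3.2 and 4.7.1).

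**4. Would the study-level hold help?** It needs 4/11 = 36% of patients with drug-related Grade 3–4 non-hematologic toxicity of any kind. If the true rate of such toxicity is assumed to be 10%, 20% or 30%, P(X ≥ 4), X ~ Bin(11, rate), is 0.019, 0.161 or 0.430. A single anaphylaxis does not trigger it.

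**5. What could a mandatory stop cost the design?** Section 7.8 continues to stage 2 with 2 or more responses among 11. The stated early-stopping probabilities (70% at a 10% response rate, 11% at 30%) reproduce as 0.697 and 0.113, so the chance of passing is 1 minus these. Suppose that one patient becomes a certain non-responder, so that X ~ Bin(10, p) and P(pass) = 1 − (1−p)^10 − 10p(1−p)^9.

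| True rate | All 11 can respond | One of 11 cannot |
|---|---|---|
| 30% | 1 − 0.1130 = 0.8870 | 1 − 0.0282 − 0.1211 = 0.8507 |
| 10% | 1 − 0.6974 = 0.3026 | 1 − 0.3487 − 0.3874 = 0.2639 |

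This is an upper bound. Section 7.5 counts as non-responders those who leave the study before a first assessment. Assessments begin at Cycle 2 Day 1, and stopping the drug need not end assessment.

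**The case against.** The strongest reply is that the plan leaves room for sound judgment. Table 1 is a recommendation. Section 4.3 lists an adverse event as a reason to discontinue. Section 4.4 permits any medication needed for safety, and Appendix D lists antihistamines, glucocorticoids and epinephrine for recurrent shock. Section 8.1.1 brings every SAE from a sub-site to the main site within 24 hours, so the Principal Investigator would normally know of a life-threatening reaction before the next dose. All of this stands. It allows a stop but does not require one, and the written default points the other way.

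Three stronger readings are tempting, and the documents do not support them:

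- A reader might infer that severe reactions are not addressed at all, or that premedication after them is barred. The preparedness text covers every grade, and Section 4.2.3 discourages routine premedication only before the first dose. What is missing is a specified regimen and a re-dosing rule, not permission to treat.
- A reader might infer that Section 4.2.3 forbids re-treatment after Grade 3–4 and so contradicts Table 1. It says nothing about those grades. A site could read a prohibition into it, but that reading is not in the text.
- A reader might infer that the protocol expects anaphylactic shock or compels re-exposure. It names shock as an example of what to watch for, and it recommends resumption without mandating it.

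The Pharmacy Manual could not be checked. Its stated scope in Section 4.1 is preparation, administration and storage.

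**Conclusion.** The point holds as a missing stop and rechallenge rule for the individual patient. For a drug-related Grade 3–4 infusion reaction or anaphylaxis, the applicable written rule recommends one further exposure after recovery: at the same dose after a first Grade 3 event, at 1.2 mg/kg after a first Grade 4 event. The first-event stop for Grade 4 neuropathy shows that Table 1 can depart from its default where that default is unsuitable.

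The conclusion assumes that the reaction is judged related to SGN-35, that it resolves, and that the site follows Table 1. How often this would arise is unknown, because the documents give no event rate. The gap concerns patient safety and consistency between sites; it does not undermine the design or analysis. It is a cheap improvement that should be made.

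**What to change.** Add an infusion-reaction exception to Table 1 and Section 4.2.4:

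1. After a Grade 4 infusion-related reaction, or anaphylaxis, with suspected relationship to SGN-35: discontinue SGN-35 permanently, with no re-treatment in cycles 9–16.
2. After a Grade 3 infusion-related reaction: re-dose only with premedication and the Principal Investigator's agreement. Section 4.2.5 already uses that approval route for delays beyond 30 days.
3. After a Grade 3–4 reaction or anaphylaxis attributed to mast cell mediator release alone, with relationship to SGN-35 judged not suspected: re-dose only with the same agreement.

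The attribution wording in items 1 and 3 keeps a mediator-release anaphylaxis from falling under both.

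The cost is a wording amendment, with no new visit or procedure. An occasional patient, possibly a responder, would stop earlier. At most, one such patient among 11 lowers the chance of passing stage 1 by 3.6 percentage points at a true 30% rate (88.7% to 85.1%) and by 3.9 points at 10% (30.3% to 26.4%).

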4.2.5 Dose Modifications

Intra-patient dose reduction to 1.2 mg/kg will be allowed depending on the type and severity of toxicity. **Table 1** describes the recommended dose modifications for study treatment-associated toxicity (toxicity with suspected relationship to SGN-35).

Peripheral Neuropathy: Peripheral neuropathy should be managed using a combination of dose delay and reduction to 1.2 mg/kg. For new or worsening Grade 2 or 3 neuropathy, dosing should be held until neuropathy improves to Grade 1 or baseline and then restarted at 1.2 mg/kg. For Grade 4 peripheral neuropathy, SGN-35 should be discontinued.

A study of brentuximab vedotin (SGN-35) in CD30-positive systemic mastocytosis with or without an associated hematological clonal non-mast cell lineage disease (AHNMD)

Neutropenia: Neutropenia should be managed by dose delays and reductions. The dose of SGN-35 should be held for Grade 3 or 4 neutropenia until resolution to baseline or Grade 2 or lower. Growth factor support should be considered for subsequent cycles in patients who experience Grade 3 or 4 neutropenia. In patients with recurrent Grade 4 neutropenia despite the use of growth factors, discontinuation or dose reduction of SGN-35 to 1.2 mg/kg may be considered.

Acute Pancreatitis: Acute pancreatitis has been identified as an important potential risk associated with brentuximab vedotin dosing. Dosing should be held until a diagnosis of acute pancreatitis has been excluded if clinically suspected.

The start of the next cycle may be delayed for up to 30 days if additional time is required for the patient to recover from study treatment-associated toxicity experienced during the current cycle (**Table 1**). Delays of greater than 30 days are prohibited without approval of the Principal Investigator of the entire study, [name].

Doses reduced for treatment-related toxicity should not be re-escalated.

If 4 out of the 11 patients experience emergent drug-related Grade 3 or 4 non-hematologic toxicity, the study will be placed on hold for safety review, and if restarted upon study amendment, the starting dose of therapy for subsequent patients would be no more than 1.2 mg/kg.

Table 1. Dose Reduction Algorithms for Non-Hematologic and Hematologic Toxicity With Suspected Relationship to SGN-35

Toxicity	Grade 1	Grade 2	Grade 3	Grade 4
Non-Hematologic	Continue at same dose level.	
Continue at same dose level, except in the event of Grade 2 neuropathy.
 
For Grade 2 neuropathy, withhold dose until toxicity is \leq Grade 1 or has returned to baseline, then reduce the dose to 1.2 mg/kg and resume treatment.
 
If Grade 2 neuropathy recurs at a dose of 1.2 mg/kg, the patient should be discontinued from study.
	
Withhold dose until toxicity is \leq Grade 1 or has returned to baseline, then resume treatment at the same dose level. ^a
 
If the toxicity has not returned to \leq Grade 1 after holding the dose for 30 days, then the patient should be discontinued from the study.
 
If the same Grade 3 toxicity recurs, withhold dose until toxicity is \leq Grade 1 or has returned to baseline, then reduce to the 1.2 mg/kg/level. ^a
 
For patients with recurrence of the same Grade 3 toxicity, the patient should be discontinued from the study.
 
For Grade 3 neuropathy, withhold dose until toxicity is \leq Grade 1 or has returned to baseline, then reduce the dose to 1.2 mg/kg and resume treatment.
 
If Grade 3 neuropathy recurs at a dose of 1.2 mg/kg, the patient should be discontinued from study.
	
Withhold dose until toxicity is \leq Grade 1 or has returned to baseline, then reduce dose to 1.2 mg/kg and resume treatment. ^a
 
If the toxicity has not returned to \leq Grade 1 after holding the dose for 30 days, then the patient should be discontinued from the study
 
For patients with recurrence of the same Grade 4 toxicity at a dose of 1.2 mg/kg, the patient should be discontinued from the study
 
For Grade 4 neuropathy, SGN-35 should be discontinued.

Hematologic	Continue at same dose level.	Continue at same dose level.	
 The dose of SGN-35 should be held for Grade 3 or 4 neutropenia until resolution to baseline or Grade 2 or lower. Growth factor support should be considered for subsequent cycles in patients who experience Grade 3 or 4 neutropenia. In patients with recurrent Grade 4 neutropenia despite the use of growth factors, discontinuation or dose reduction of SGN-35 to 1.2 mg/kg may be considered. Dose interruption for anemia will not be undertaken. If patients have Grade 2 to 3 of these events at baseline only Grade 4 cytopenias suspected to be related to study drug will be considered as hematologic toxicity. ^b Obtain weekly labs until lab returns to baseline or Grade 2. G-CSF for treatment of neutropenic fever may be used, but not for treatment of neutropenia alone, nor for infection prophylaxis in the setting of neutropenia. 	

^a Patients who develop emergent Grade 3 or 4 electrolyte laboratory abnormalities will have the dose of SGN-35 reduced to 1.2 mg/kg in subsequent cycles. If the same Grade 3 or 4 electrolyte abnormalities re-occur, SGN-35 will be discontinued.

^b Patients who develop Grade 3 or 4 lymphopenia may continue study treatment without interruption.

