1.2 SGN-35 (brentuximab vedotin)

Brentuximab vedotin (SGN-35) is a CD30-directed antibody-drug conjugate (ADC) consisting of three components: 1) the antibody cAC10, specific for human CD30, 2) the highly potent antimicrotubule agent monomethyl auristatin E (MMAE), and 3) a protease-cleavable linker that covalently attaches MMAE to cAC10. The biological activity of brentuximab vedotin results from a multi-step process. Binding of the ADC to CD30 on the cell surface initiates internalization of the ADC-CD30 complex, which then traffics to the lysosomal compartment. Within the cell, a single defined active species, MMAE, is released via proteolytic cleavage. Binding of MMAE to tubulin disrupts the microtubule network within the cell, induces cell cycle arrest, and results in apoptotic death of the CD30-expressing tumor cell.

Two phase 2 studies evaluating the efficacy and safety of brentuximab vedotin as a single agent were performed in patients with relapsed or refractory Hodgkin lymphoma (HL) and systemic anaplastic large cell lymphoma (ALCL). In the pivotal phase 2 study of relapsed or

refractory HL, 75% of patients had an objective response (complete or partial remission) with median duration of approximately 7 months. One-third of patients achieved a complete response (CR). In the phase 2 study of relapsed or refractory systemic ALCL, the objective response rate (ORR) was 86%. Due to few events of progression or death, the median duration of objective response was not estimable; however, the lower limit of the 95% confidence interval (CI) was 36 weeks. Over 50% of patients achieved a CR. Nearly all patients (>90%) in both studies experienced a reduction in tumor volume.

Treatment-emergent adverse events (AEs) occurring in $\geq 20\%$ of HL and systemic ALCL patients in the phase 2 studies were peripheral sensory neuropathy (44%), fatigue (42%), nausea (41%), diarrhea (34%), pyrexia (31%), upper respiratory tract infection (28%), neutropenia (21%), and vomiting (20%). These events were primarily Grade 1 or 2, with the exception of neutropenia, for which Grade 3 and Grade 4 events were reported for 13% and 7% of patients, respectively. Similar patterns and incidences of AEs were generally observed for HL and ALCL patients.

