4.4 Concomitant therapy

In general, the use of any concomitant medication/therapies deemed necessary for patient supportive care and safety are permitted provided they are documented in the patient records. A list of medications which may be used to treat mediator-related symptoms are listed in **Appendix D**. All medications taken within 30 days of the first dose of study drug and all concomitant medications/therapies must be recorded on the Concomitant/Non-Drug Therapy CRF.

Women will avoid breast-feeding, and all women of childbearing potential will be required to use barrier contraception for the duration of the study and for 3 months post study.

Other anti-cancer agents including chemotherapy, radiation therapy, or biologic response modifiers are not permitted during the study. No other investigational drug is allowed during the study. Hematopoietic growth factors are not permitted during study (except G-CSF for neutropenic fever). Prophylaxis may be used for the prevention of nausea and vomiting and is at the discretion of the investigator.

Other anti-cancer agents including chemotherapy, radiation therapy, or biologic response modifiers are not permitted during the study. The exception is the use of hydroxyurea to control a proliferative leukocyte count related to a concurrent myeloid neoplasm (eg, CMML, or other MDS/MPN, or MPN associated with advanced SM). No other investigational drug is allowed during the study. Hematopoietic growth factors are not permitted during the study.

(except G-CSF for neutropenic fever). The exception is the use of erythropoiesis stimulating agents (with or without IV iron) in patients who are Jehovah's witnesses and for religious reasons are not permitted to undergo treatment with blood products. Prophylaxis may be used for the prevention of nausea and vomiting and is at the discretion of the investigator.

During treatment with SGN-35, glucocorticoids can be used in the event of appropriate need, as outlined in **Appendix D**, "Mediator Drugs to Ameliorate Symptoms Related to Systemic Mastocytosis."

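### Section 4.2.5, Table 1 and section 4.4 give conflicting instructions on growth factors, and 4.4 prints two versions of its prohibited-therapy paragraph; one consistent instruction is needed

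*Combined protocol and SAP*

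**What the plan says.** Four places bear on growth factor use during treatment.

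- **Section 4.2.5, Neutropenia paragraph.** "Growth factor support should be considered for subsequent cycles in patients who experience Grade 3 or 4 neutropenia". The next step applies "In patients with recurrent Grade 4 neutropenia despite the use of growth factors", when stopping or reducing the study drug may be considered.
- **Table 1, hematologic row, Grade 3 and 4.** The cell repeats both statements. It then says that G-CSF may be used for neutropenic fever, "but not for treatment of neutropenia alone, nor for infection prophylaxis in the setting of neutropenia".
- **Section 4.4, prohibited therapy, first printing.** "Hematopoietic growth factors are not permitted during study (except G-CSF for neutropenic fever"; the sentence ends there. Other anti-cancer agents are barred without exception.
- **Section 4.4, prohibited therapy, second printing.** The same bans reappear, now with two additions. On anti-cancer agents: "The exception is the use of hydroxyurea to control a proliferative leukocyte count related to a concurrent myeloid neoplasm". On growth factors: "The exception is the use of erythropoiesis stimulating agents (with or without IV iron" and so on, limited to patients who "for religious reasons are not permitted to undergo treatment with blood products".

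Section 3.3.2 excludes patients given growth factor support in the 14 days before Day 1. That governs entry and does not settle what is allowed on study.

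**The concern.** Neutropenia is the event that section 1.2 singles out as an exception to a mainly Grade 1 or 2 toxicity profile, so the growth factor instruction is likely to be used. If it points both ways, two patients with the same event can receive different support depending on which section the site follows. The same act can also be classed as following the protocol or as a deviation from it. The trial has a main site and at least one sub-site (8.1.1), and audits check adherence to the protocol (8.2.2), so a deviation needs one meaning across sites. With 11 patients in the first stage, even a few inconsistently managed patients would complicate the reading of the neutropenia and dose-modification data.

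**Working it through.** **Passages applied to cases.** The plan gives no figure for growth factor use, so the check is to apply each instruction to the situations a site would meet.

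1. *Grade 3 or 4 neutropenia with fever, G-CSF given for the fever.* Table 1 allows it, 4.4 allows it, and 4.2.5 is silent on fever. No conflict.
2. *Grade 3 or 4 neutropenia without fever, growth factor given in a later cycle.* The 4.2.5 paragraph and the first part of the Table 1 cell suggest it; their trigger is grade, with no mention of fever. The last part of the same cell excludes G-CSF here, and both printings of 4.4 exclude it. Direct conflict.
3. *The same patient, support considered and not given.* No passage is breached, because the first instruction asks only for consideration.
4. *Recurrent Grade 4 neutropenia in a patient who has never been febrile.* The step in 4.2.5 and Table 1 is worded for recurrence despite growth factors. Under 4.4 this patient could not have received them, so the text does not say whether the step applies.
5. *A myeloid neoplasm with a rising leukocyte count, hydroxyurea wanted.* Barred if the first printing of 4.4 is read alone, since the second printing treats hydroxyurea as an exception to the anti-cancer ban. Allowed under the second.
6. *A patient who cannot accept blood products, erythropoiesis-stimulating agent wanted.* Barred under the first printing, allowed under the second.

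Case 2 is the contradiction and case 4 is its consequence. Cases 5 and 6 arise from the duplicated paragraph.

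**Illustration of frequency.** Section 1.2 describes neutropenia in patients with Hodgkin lymphoma or systemic anaplastic large cell lymphoma, "for which Grade 3 and Grade 4 events were reported for 13% and 7% of patients" respectively, with 21% at any grade.

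- Assumption: these are worst grades per patient. Then 13% + 7% = 20%, which fits within 21%.
- Assumption: the rate carries over to systemic mastocytosis. Expected patients with a Grade 3 or 4 event: 11 × 0.20 = 2.2 in the first stage and 26 × 0.20 = 5.2 if both stages run. Chance of at least one among 11: 1 − 0.80^11 = 91%.
- Alternative: Table 1 counts only Grade 4 cytopenias as toxicity when Grade 2 to 3 is present at baseline. With 7% instead: 11 × 0.07 = 0.77, and 1 − 0.93^11 = 55%.

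Neither figure is a bound. The rates come from another disease, and patients who start with low counts need a smaller fall to reach Grade 4. The counts also include febrile patients (case 1) and events in the last cycle, which has no later cycle.

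**The case against.** The strongest reply is that the passages can all be obeyed. The first instruction only asks that support be considered, and a patient given G-CSF for fever can later have recurrent neutropenia despite growth factors. That is correct. A reader might infer that no site can comply with all of the passages; the documents do not support this, as case 3 shows. What remains is that the text suggests an act in one place and prohibits it in another, and nothing elsewhere says which governs.

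A second reply is that the repeated paragraph in 4.4 reads as a general rule followed by labelled exceptions, and is probably leftover text. That is a fair reading and makes this part a matter of tidying. It still needs doing, because the first printing stands as a complete rule without the exceptions.

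A reader might go further and infer that responses reached during supportive treatment inflate the response rate, so that the stated error rate fails or responses must be recounted. It is true that Appendix G asks for other causes to be excluded only before progression or loss of response is assigned, and that 7.5 links no medication to response. But:

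- Section 7.8 sets its null rate as a response rate per the consensus criteria, which attach no such condition to the blood-count improvements. At that counted rate the exact two-stage calculation gives 8.65%, matching the stated 8.7%.
- Larger values appear only if misattribution is imposed. Forcing one such response among the first 11 gives 21.7%, but the documents give no rate for this.
- The route is narrow: baseline neutrophils below 1 × 10^9/L or hemoglobin below 10 g/dL, disease-related damage only, and 12 weeks of maintained improvement.
- No passage links hydroxyurea to spleen size.

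**Conclusion.** The point holds as an internal inconsistency that is wrong as written. Confidence is high, because it rests on complete sentences in the current text and on no assumption about rates. Giving growth factor to an afebrile patient with earlier Grade 3 or 4 neutropenia is suggested by 4.2.5 and part of Table 1, and ruled out by the rest of that cell and by 4.4. The two printings in 4.4 differ on hydroxyurea and erythropoiesis-stimulating agents. The consequence is uneven management and unclear deviation calls, not impossible compliance and not a demonstrated error in the primary analysis.

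The size in this population is unknown. About 2 of the first 11 patients is an illustration that depends on the worst-grade reading and on carry-over from lymphoma.

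**What to change.** By amendment, reconcile the Neutropenia paragraph of 4.2.5, the hematologic cell of Table 1 and the two printings in 4.4, so that one consistent instruction stands for growth factors, erythropoiesis-stimulating agents and hydroxyurea. The wording of the recurrent Grade 4 step should agree with it, and the prohibited-therapy paragraph should appear once. What the instruction says is for the sponsor to decide; this review does not prefer one.

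The cost is more than an edit. The change is not administrative, so it needs ethics committee approval (8.3.1), and the drug supplier must be notified of the amendment (8.2.1). Waiting for the amendment that 7.8 foresees for the second stage would leave the conflict in place for the first 11 patients. No change to the endpoint, the 2 of 11 and 5 of 26 thresholds, or the analysis is needed.
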